Title: My MS and My Menstrual Cycle

Measuring MS symptoms in relation to menstrual cycles: exploring how MS symptoms may be affected at different times during a menstrual cycle in females living with Multiple Sclerosis

Research Team:

[name], [name], [name], [name], [name], [name], [name], [name], [name], [name], [name].

Objective:

To evaluate the severity and timing of MS symptoms with timing of menstrual cycles in women living with MS.

Methods:

Design:

This project is a prospective observational study of females living with MS, tracking MS symptoms in correlation with time of menstrual cycle, measured and correlated via a smartphone app

Inclusion Criteria:

Participants are required to meet the following criteria:

- Females with diagnosed MS by 2024 McDonald Diagnostic criteria ¹ (biologically sex-based, any gender as long as not on hormonal gender-enhancing therapy)
- ages 16+, still experiencing menstruation with cycles of 23 to 36 days spacing
- have entered menarche, are experiencing menstrual cycles, and have not yet entered menopause
- participants may utilize hormonal contraceptive methods, such as oral contraceptive methods or hormonal IUDs
- English-speaking
- Willing to provide informed consent, mature minors will provide informed consent, their physician will determine whether their level of maturity is appropriate to participate in the study and complete consent as a mature minor
- Have the ability to complete questionnaires and operate the app

Exclusion Criteria:

People will be excluded as per the following criteria:

- diagnosed with CNS inflammation disorders other than MS such as:
 - NMOSD (Neuromyelitis Optica Spectrum Disorder)
 - MOGAD (Myelin Oligodendrocyte Glycoprotein Antibody-associated Disease)
- male or intersex individuals, given the inclusion criteria of requiring a uterus
- females < 15 years of age
- females who have not started menstruation
- females who have stopped menstruation due to menopause or hysterectomy
- pregnant or postpartum women < 1 year after delivery and/or people who currently breastfeeding
- are unable to provide informed consent, or are not deemed a mature minor to complete consent are unable to complete questionnaires and operate the app

Recruitment:

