Via treating neurologists (MS clinic or community-based) and/or nurse practitioners; flyers sent through social media newsletters MS Canada and MS research portal via MS Canada and in clinic rooms/waiting rooms neurologists' practices; mass secure patient messaging via connectcare electronic medical records system

Randomization:

n/a

Intervention:

Eligible patients will download the My Normative app, by scanning a link/QR code. Once registered, electronic consent will be collected through the app. Participants will fill out a baseline series of demographics in addition to a series of patient-reported outcome measures (fatigue, patient perceived level of disability, MS patient symptoms screen, sleep, self-efficacy scale, self-perceived cognition and coping levels, motivation for cognition, and depression and anxiety levels) on the app, as well as enter information re: menstrual cycle tracking/hormone levels as prompted by the app. Participants will then track their menstrual cycles for 6 months with completion of patient reported outcome measures: (1) fatigue – MFIS – 5 item;²⁻⁴ (2) depression & anxiety - HADS;⁵ (3) coping (mini-COPC); (4) MFC – motivation for cognition;⁶ (5) MSymptoscreen (screen of common MS symptoms)⁷ and likert scale from 0 to 7 as to self-perceived cognition levels. This will be done five times per month, as per the different phases of the menstrual cycle. At the end of 6 months, participants will complete an exit scale – with all of the above.

Duration of Study Involvement:

6 months (this has been determined to be optimal in capturing 3 months of menstrual cycles)

This study will be a 2 year study with rolling enrollment

Primary outcomes:

Difference in modified MFIS (fatigue) levels, 5 items during menstruation compared to other times of the menstrual cycle ^{3, 4, 8-10}.

Secondary outcomes:

Qualitative self-reported difference:

- **HADS** (Hospital anxiety and depression scale) – 14 items ⁵
- **MNSQ** (Multiple Sclerosis Neuropsychological Screening Questionnaire–Patient Version) - 15 items ¹⁰⁻¹³
- **Two Likert scale** – self perceived cognition levels (0 to 7)
- **Coping** – MS specific – Brief COPE Short Version (Mini-Cope) – 12 items (3 different coping styles: active/adaptive, avoidant/maladaptive, and emotional/neutral ¹⁴)
- **MFC scale** (motivation for cognition)⁶

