A recent prospective study examining MS symptom severity variability at points throughout women's menstrual cycle was published in 2023; participants reported a number of symptoms at different points during their menstrual cycles and there was a suggestion of less fatigue as measured by the MFIS during the perimenstrual period as compared to the luteal period, not felt to be clinically significant, as well as less variability in fatigue reported by women on continuous hormonal oral contraception compared to those who weren't. The authors conclude that more studies are needed to examine the possible relationship between menstruation and MS symptoms.⁴²

The My Normative platform app has been used in other populations to track menstrual cycles in relation to various symptoms for women in the general population and other conditions.(mynormative.ca) We hope to examine MS-related symptoms to stages of the menstrual cycle, as measured by the My Normative platform.(mynormative.ca) We hypothesize that MS-related fatigue would be greater in the luteal phase of the cycle as compared to other times of women's menstrual cycles, as measured by the MFIS-5 item.³ Secondary outcomes will include impact of menstrual cycle stage upon cognition as measured by the likert scale of self-perceived cognitive levels from 1 to 7, various MS symptoms as measured by the SymptoMScreen (walking, hand function/dexterity, spasticity & stiffness, bodily pain, sensory symptoms, bladder control, fatigue, vision, dizziness, cognition function, depression, anxiety),⁷ MFC scale (motivation for cognition)⁶ and coping (the mini-cope)¹⁴ over a 6 month period with a minimum of 3 months of menstrual cycle tracking. The My Normative platform tracks menstrual cycles in five phases: (1) menstrual phase; (2) follicular phase; (3) ovulation phase; (4) Luteal phase early; (5) luteal phase late

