2.0 Proposed Research

Hypothesis:

Women with MS experience worsening of fatigue, as self-reported by MFIS, during menstruation compared to other times during their menstrual cycles.

Design:

Prospective observational self-enrolled study on mobile app.

Setting:

online, app reporting

Subjects:

Females living with MS, who experience menstruation.

Inclusion Criteria:

Participants are required to meet the following criteria:

- Females with diagnosed MS by 2017 McDonald criteria ¹ (biologically sex-based, any gender as long as not on hormonal gender-enhancing therapy)
- ages 16+, still experiencing menstruation with cycles of 23 to 36 days spacing
- have entered menarche, are experiencing menstrual cycles, and have not yet entered menopause
- participants may utilize hormonal contraceptive methods, such as oral contraceptive methods or hormonal IUDs
- English-speaking
- Willing to provide informed consent, mature minors will provide informed consent, their physician will determine whether their level of maturity is appropriate to participate in the study and complete consent as a mature minor
- Have the ability to complete questionnaires and operate the app

Exclusion Criteria:

People will be excluded as per the following criteria:

- diagnosed with other CNS inflammation disorders than MS
- male or intersex individuals, given the inclusion criteria of requiring a uterus
- females < 15 years of age
- females who have not started menstruation
- females who have stopped menstruation due to menopause or hysterectomy

- pregnant or postpartum women x 1 year after delivery and/or people who currently breastfeeding
- are unable to provide informed consent
- are unable to complete questionnaires and operate the app

Randomization:

n/a

Questionnaires:

Baseline:

- **PDDS** – single scale (physical disability measure) Patient Determined Disease Steps ⁴³
- **Full MFIS** – Modified Fatigue Impact Scale (21 point scale) – fatigue ^{2, 8, 9}
- **HADS** (anxiety & depression) – Hospital Anxiety & Depression Scale (14 items)⁵
- **PHQ9** – Patient Health Questionnaire (depression & anxiety) (9 items)^{44, 45}
- **MSNQ** (cognition) (15 item)¹¹⁻¹³
- **Mini Cope** (coping) (12 item)⁴⁶
- **Pittsburgh sleep quality index** (sleep quality) (24 items)⁴⁷
- **the SymptoMScreen** (12 item) (walking, hand function/dexterity, spasticity & stiffness, bodily pain, sensory symptoms, bladder control, fatigue, vision, dizziness, cognition function, depression, anxiety)^{7, 42}

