- **MFC scale** (Motivation for Cognition) (10 item)⁶
- **General factors**
 - Demographics (age, race, ethnicity, marital status, level of education, # children, working outside/inside home), BMI, smoking status
 - Years since onset MS (first symptoms) and diagnosis
 - Disease modifying therapies list
 - Medications listt
- **Menstrual cycle information**
 - Length of cycle
- **Type of contraception**
 - Rhythm method
 - No contraception
 - Barrier
 - Condoms
 - Diaphragm
 - IUD (with hormone, without hormone)

- OCP – type – continuous/not continuous
- **5 time points during the menstrual cycle**
 - 1) Follicular phase, during active menstruation
 - 2) Follicular phase, no menstruation (leading up to ovulation)
 - 3) ovulation phase
 - 4) Luteal phase, first half
 - 5) Luteal phase, second half (this is the 5-7 days before the next period starts)

Each time point:

- MFIS brief 5 item ³
- Cognition Likert scale – self perceived cognition levels (0-7)
- SymptoMSScreen 12 item ⁷
- Mini-COPE (12 item)¹⁴
- MFC scale (motivation for cognition) 10 item⁶
- Longer MFIS point scale once per cycle, alternating timing of long scale done at each time point (3 points within cycle) over study duration (6 months) ^{2, 8, 9}

Study Completion:

- **PDDS** – single scale (physical disability measure) Patient Determined Disease Steps⁴³
- **Full MFIS** – modified fatigue Impact Scale (21 point scale) – fatigue^{2, 8, 9}
- **HADS** (anxiety & depression) – Hospital Anxiety & Depression Scale – 14 items ⁵
- **PHQ9** – patient health questionnaire (depression & anxiety) – 9 items ^{44, 45}
- **MSNQ** (cognition) 15 item ¹¹⁻¹³
- **Cognition Likert scale** – self-perceived cognition levels (0 – 7)
- **Mini Cope** (coping) (12 item) ⁴⁶
- **Pittsburgh sleep quality index** (sleep quality) 24 items ⁴⁷
- **the SymptoMSScreen** - 12 item (walking, hand function/dexterity, spasticity & stiffness, bodily pain, sensory symptoms, bladder control, fatigue, vision, dizziness, cognition function, depression, anxiety) ⁷
- **MFC scale** (motivation for cognition) – 10 item ⁶
- Relapses in past 6 months/use of steroids
- Optional - agreement to be contacted to participate in qualitative interview re: use of app

Sample size:

There is not much information or data to calculate sample size. We plan to recruit 300 women living with MS for this study as a convenience/availability sample from the two

MS Clinics at the University of Alberta and University of Calgary (approximately 150 per site).

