What this study adds:

Despite the longstanding knowledge of MS risk, onset, and inflammatory activity being related to different hormonal periods throughout women's lives, there is still much that is unknown about the interactions and relationship of female hormones and different

female hormonal states upon MS. In addition, women with MS often report MS symptoms as fluctuating in severity at different points throughout their menstrual cycles. However, despite reporting, literature has not shown definitive correlations between MS symptom severity in relation to different points in the menstrual cycle. If we are able to establish correlations between common MS symptoms at particular points in the menstrual cycle, this will aid researchers, clinicians, and women living with MS around examining different strategies to try to treat MS symptom severity at different points throughout the menstrual cycle. This could include strategies such as that seen with perimenstrual migraine, where women enact prophylactic strategies around the time of menstruation to minimize their migraine headaches during that time of the cycle.⁴⁸

Methodologic Issues:

Patients will self-enroll in the study, through accessing and downloading the app as per instruction. Participants download the My Normative App and become a registered user. Once registered, they will read the consent and then sign consent if they wish to participate in the study. Participants will have the option of withdrawing from the study at any time by simply not responding to cues from the app to fill out their questionnaires. Participants are provided with contact information for the study team, and can withdraw from the study by contacting the study team.

References:

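### Late luteal is defined by a period that has not yet started, and the plan has no rule for deriving phase; assign phase retrospectively from recorded bleeding dates

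*Combined protocol and SAP*

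**What the plan says.** Under 2.0 Proposed Research (Questionnaires), the cycle is divided into five time points. The first is the part of the follicular phase with active bleeding. The fifth is "Luteal phase, second half (this is the 5-7 days before the next period starts").

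The design is a "Prospective observational self-enrolled study on mobile app". On the repeated questionnaires, Methods (Intervention) states: "This will be done five times per month, as per the different phases of the menstrual cycle". Methodologic Issues shows that the app triggers them, since a participant can withdraw "by simply not responding to cues from the app to fill out their questionnaires". The only statement on where the phase label comes from is in 1.0 Background and Rationale: "The My Normative platform tracks menstrual cycles in five phases".

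The Analytical Plan uses cycle phase as the grouping factor in the tests and as a predictor in the regression. It gives no rule for deriving phase. Its sensitivity analysis is described in general terms and does not mention phase.

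Two hypotheses depend on the label. The primary outcome and the stated hypothesis compare fatigue on the MFIS-5 during menstruation with the rest of the cycle. The Background instead expects that "MS-related fatigue would be greater in the luteal phase of the cycle as compared to other times".

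**The concern.** When a woman answers a late-luteal questionnaire, the event that defines late luteal has not happened. Any label fixed at that moment is a forecast. If the next period comes later than forecast, the rating may belong to an earlier phase. If it comes sooner, the rating may have been given while she was already bleeding.

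Phase is the exposure in this study, and the boundary between late luteal and menstruation separates its two hypotheses. The pilot study that the protocol cites reported its fatigue signal across much the same boundary, perimenstrual against luteal. Ratings on the wrong side pull the two phase means together, so the error works mainly towards finding no difference.

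**Working it through.** **No figure in the plan to reproduce.** The documents give no prediction error, no within-woman cycle variability and no power calculation. The sizes below therefore rest on an assumed error and are shown as a range.

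**Inputs**
- Window length w: 5 or 7 days, from the definition of time point 5.
- Prediction error of the next period start: normal, mean 0, SD s = 1 to 5 days (assumed).
- Contrast for illustration: 0.25 SD (assumed).

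**Step 1: share mislabelled, cue at mid-window.** A rating is mislabelled if the error exceeds half the window in either direction: m = 2 × [1 − Φ((w/2)/s)]. By symmetry, m/2 falls after bleeding began. Example for w = 5, s = 3: 2 × [1 − Φ(0.833)] = 0.405.

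| s (days) | w = 5: mislabelled | of which after onset | w = 7: mislabelled | of which after onset |
|---|---|---|---|---|
| 1 | 1.2% | 0.6% | 0.05% | 0.02% |
| 2 | 21% | 11% | 8% | 4% |
| 3 | 40% | 20% | 24% | 12% |
| 4 | 53% | 27% | 38% | 19% |
| 5 | 62% | 31% | 48% | 24% |

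**Step 2: cues spread evenly over the window.** Here the cue falls k = 1, …, w days before the predicted start and the error is rounded to whole days. A rating is truly late luteal if it lies 1 to w days before the actual start. Averaged over k, for s = 1, 2, 3, 4, 5:
- Truly late luteal: 85, 69, 55, 44, 37% (w = 5); 89, 77, 66, 56, 48% (w = 7).
- Given after bleeding began: 8, 16, 23, 28, 32% (w = 5); 5, 11, 17, 22, 26% (w = 7).

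**Step 3: effect on each contrast.** All other labels are taken as correct.

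(a) *Late luteal versus menstrual, fatigue raised only in late luteal.* The fraction retained equals the share correctly labelled. From Step 2 this is 37–89% over the whole range, and 55–77% at s = 2–3.

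(b) *Menstrual versus late luteal, fatigue raised only in menstruation.* The fraction retained is 1 minus the share after onset. It runs from 1 − 0.055 = 0.945 (w = 7, s = 1) to 1 − 0.315 = 0.685 (w = 5, s = 5).

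(c) *Pooled luteal phase, as the Background hypothesis is worded.* With an equal effect in both luteal halves and equal weights, a rating taken too early is treated as still luteal. Only the after-onset half of the errors counts, in one of two luteal time points, so the fraction retained is 1 − (m/2)/2. At the worst (w = 5, s = 5): 1 − 0.309/2 = 0.846, and 0.25 × 0.846 = 0.21 SD. At s = 1 the contrast stays at about 0.25 SD.

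(d) *Primary contrast, menstruation versus the mean of the other four phases, fatigue raised only in menstruation.* Late luteal is one of four comparators, so the fraction retained is 1 − (share after onset)/4. With cues spread over the window this runs from 1 − 0.315/4 = 0.92 (w = 5, s = 5) to 1 − 0.055/4 = 0.99 (w = 7, s = 1).

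**Step 4: reading of the window.** The definition can also be read as days 7 to 5 before the period rather than a window of 5 to 7 days. Under that reading a mid-window cue is correct 87, 55, 38, 29 and 24% of the time for s = 1 to 5.

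**The case against.** The app may already relabel ratings once the next period is logged, and nothing says that it would issue a late-luteal cue after bleeding has been entered. This stands as a limit: that labels are fixed at the cue is a condition of the point, not a statement in the documents. But no section describes relabelling either. A protocol whose exposure is phase should state its own rule; if the app does relabel, one sentence settles it.

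The size is assumed. This also stands. A reader might infer a large prediction error from the entry criterion "still experiencing menstruation with cycles of 23 to 36 days spacing". That is a range between women and says nothing about how far one woman's next period departs from its forecast. Usual cycle length is collected at baseline, so the forecast could be individual. At an SD of 1 day with a mid-window cue the problem almost vanishes.

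A reader might also infer that the Background's luteal hypothesis loses most of its effect. Applying the full mislabelled share to 0.25 SD gives as little as 0.25 × (1 − 0.62) = 0.10 SD, but that fits only an effect confined to late luteal. The hypothesis covers the whole luteal phase, and a late-luteal rating taken a few days early is usually still luteal. Nor do the documents support the reading that the primary comparison is seriously compromised: active bleeding is directly observable, and late luteal is only one of four comparator phases.

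**Conclusion.** The point holds as a correction that should be made before analysis; it is not a fatal flaw. Late luteal is defined by a future event, ratings are collected before that event, and the plan does not say how phase is assigned.

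If the label at the cue is used, the comparisons most at risk are late luteal versus menstruation and the other phase-by-phase contrasts. At an error SD of 2–3 days with cues spread over the window, an effect confined to late luteal would be seen at 55–77% of its size. The pooled luteal hypothesis is affected modestly and the primary contrast little. These figures rest on an assumed normal error with SD 1–5 days, correct labels in the other phases, and the effect patterns named in the working. The direction and the ordering of the contrasts are firmer than the percentages.

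**What to change.** Require the date of each rating and all bleeding dates to be stored. Six months of cycle tracking implies that bleeding dates are recorded, but the protocol does not say so. Then add to the Analytical Plan:

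- For the main analysis, phase is assigned retrospectively. Menstrual means logged bleeding days. Late luteal means a single fixed number of days, stated in advance, counted back from the next recorded period start.
- A non-bleeding rating that falls before that window takes the platform's preceding phase (early luteal if it was labelled late luteal).
- A rating with no later recorded start (the last incomplete cycle, or hormonal contraception without regular bleeds) keeps the platform label in the main analysis, is flagged, and is excluded in a sensitivity analysis.
- Derived labels are cross-tabulated against platform labels, and the analysis is repeated with the platform labels.

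The cost is a few lines of derivation code, provided the dates are held. The limits are that flagged ratings cannot be relabelled, some cycles will have no late-luteal rating or two ratings in one phase, and the ovulation and early-luteal boundaries remain estimated.

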Taylor et al completed a pilot study, published in 2023, on menstrual cycle and fatigue symptoms in eumenorrheic women living with MS. There was a suggestion of less fatigue in the perimenstrual period compared to the luteal portion of the cycle, and less fluctuation in symptom severity over the cycle for women on continuous hormonal oral contraception. There was a lot of difficulty recruiting for this study with over 200 women contacted and 70 enrolled and 47 providing more than 4 weeks of data for a 6 month period.⁴² Despite the challenges faced by these authors, and anticipating a 20% dropout, we plan to try to recruit a maximum of 300 participants over 2 years. There are no substantial prior studies to base the sample size calculation upon.

Analytical Plan:

We will calculate summary statistics for primary and secondary outcomes across different menstrual cycle phases. We will conduct hypothesis tests (e.g., t-tests, ANOVA) to determine if there are statistically significant crude differences in MS symptom severity or relapse rates among different menstrual cycle phases and explore the relationship between the timing of the menstrual cycle and MS symptom severity using correlation coefficients (e.g., Pearson's correlation). We will perform regression analysis to identify any potential predictors of MS symptom severity, including menstrual cycle phase, age, duration of MS, and other relevant covariates and stratify the analysis by age groups to explore for effect modification by reproductive stage of youth, early adulthood (reproductive years) and later adulthood (peri-menopause), respectively defined as participants < 20 years old, 20 to 40 years old, > 40 years old. We will control for potential confounding variables, such as medication use, comorbidities, and lifestyle factors, in these adjusted models. Finally, we will perform sensitivity analysis to assess the robustness of the results by varying assumptions or analytical methods. Finally, we will provide descriptive measures of baseline characteristics/demographics.

Feasibility:

This study will be carried out through the reciprocal ethics process at the Universities of Alberta and Calgary. Each MS Clinic at each clinic follows about 5000 PwMS in Alberta. MS affects 3 women to every man, with average onset between ages 20 to 40. Therefore, both clinics see many women with MS who are at ages who experience menarche.

Timelines:

2 years, each site to recruit 150 participants maximum

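### The analyses estimate only average phase differences, overall or within age strata; a woman-specific menstruation effect and a phase-by-contraception term would be a cheap exploratory addition

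*Combined protocol and SAP*

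**What the plan says.** The hypothesis in section 2.0 is stated for women with MS as a group: "Women with MS experience worsening of fatigue, as self-reported by MFIS, during menstruation compared to other times during their menstrual cycles". The Analytical Plan in the same section lists these steps:

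- Summaries: "We will calculate summary statistics for primary and secondary outcomes across different menstrual cycle phases".
- Tests: "We will conduct hypothesis tests (e.g., t-tests, ANOVA) to determine if there are statistically significant crude differences in MS symptom severity".
- Correlation: "explore the relationship between the timing of the menstrual cycle and MS symptom severity using correlation coefficients".
- Regression: "We will perform regression analysis to identify any potential predictors of MS symptom severity, including menstrual cycle phase, age, duration of MS", with adjustment for confounders.
- Effect modification: the plan will "stratify the analysis by age groups to explore for effect modification by reproductive stage", in three age bands (under 20, 20 to 40, over 40).
- Sensitivity analyses whose content is not specified.

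No step names a phase contrast for each woman, a random phase effect, or the SD of that effect between women. Age is the only named effect modifier. Contraception is recorded at baseline, including hormonal or non-hormonal IUD and continuous or non-continuous oral contraceptive. The Sample size section reports that the cited pilot suggested "less fluctuation in symptom severity over the cycle for women on continuous hormonal oral contraception". The design calls for five measurements per cycle over 6 months, with at least 3 months tracked.

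**The concern.** A mean phase difference is one number for all women, or one per age band. It cannot separate a modest effect shared by everyone from a large effect in a few, and it cannot show effects in opposite directions. The protocol gives some reason to expect differences between women: the pilot's contrast was by contraceptive use, and users of hormonal contraception are eligible. Under What this study adds, the protocol also offers perimenstrual migraine as a model, "where women enact prophylactic strategies around the time of menstruation". How useful such a timed strategy would be depends partly on how consistent and how widely shared the pattern is.

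Because each woman contributes several cycles, true variation between women can be separated from occasion-to-occasion noise. With one cycle it cannot. The plan collects the data needed and does not use them for this. There is also a consequence for the mean itself: a within-woman regression that leaves out real variation in the phase effect gives too narrow an interval.

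**Working it through.** **Inputs from the document.** Maximum 300 women; 20% dropout leaves 300 × 0.8 = 240. Pilot retention was 47/70 = 67%, or about 201 of 300. There are five measurements per cycle, one menstrual and four other. With cycles of 23 to 36 days, 3 months hold about 2.5 to 4.0 cycles and 6 months about 5.1 to 7.9, so 3 and 6 cycles are used below. The plan gives no alpha, power, effect size or SD, so it has no figure of its own to reproduce.

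**Assumptions.** Two-sided 5% for the mean and one-sided 5% for the variance. Effects are in units of the within-woman occasion-to-occasion SD. Errors are independent and normal, and all k cycles are complete.

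**Per-woman contrast** (menstrual minus the average of the other four phases, over k cycles): variance = 1/k + 1/(4k) + τ² = 1.25/k + τ², where τ is the between-woman SD of the effect.

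**Minority scenario: 20% at +1, the rest at 0.**
- Mean = 0.2 × 1 = 0.20. τ = √(0.2 × 0.8) = 0.40.
- At 201 women and 3 cycles, the contrast SD = √(0.4167 + 0.16) = 0.759 and SE = 0.759/√201 = 0.0536. Then 0.20/0.0536 = 3.73, and power for the mean = Φ(3.73 − 1.96) = 96%.
- The average is detected, at one fifth of the size in affected women.

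**Cancelling scenario: 25% at +1, 25% at −1, half at 0.**
- Mean = 0. τ = √0.5 = 0.71. A valid test of the mean rejects at its 5% error rate.

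**Power to detect τ, 201 women, 3 cycles.** The F-test compares per-woman means with the cycle-to-cycle contrasts, on 200 and 402 degrees of freedom (critical value 1.219). Under the alternative F is scaled by 1 + kτ²/1.25.

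| Scenario | τ | Scale factor | Power |
|---|---|---|---|
| 20% at +1 | 0.40 | 1.384 | about 85% (84% in simulation) |
| 25% at +1, 25% at −1 | 0.71 | 2.20 | over 99% |
| 20% at +0.5 | 0.20 | 1.096 | about 19% |

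Treating the error variance 1.25/k as known would give 94.5% in the first row, but it has to be estimated. At 6 cycles the weak-minority power rises only to about 50%. With serial correlation of 0.3 between successive occasions (AR(1)), power in the first row falls to about 55 to 79%, depending on the test.

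**Error rate for the mean if the variation is ignored (cancelling scenario).** Take a within-woman model with no random phase effect.
- Its residual variance is about 1 + 0.8kτ²/(5k − 1): 1.086 at k = 3 and 1.083 at k = 6.
- The contrast variance it uses is 1.25/k times that: 0.452 and 0.226. The true variances are 0.917 and 0.708.
- SE ratios are √(0.452/0.917) = 0.70 and √(0.226/0.708) = 0.56. A nominal 5% test therefore rejects about 17% and 27% of the time; simulation gave 17% and 28%. Using per-woman contrasts instead gave 5 to 6%.

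**Labelling individual women.** The SE of one woman's own contrast is √(1.25/k): 0.65 at 3 cycles and 0.46 at 6. Flagging at one-sided 5% when 20% are truly affected by 1 SD has sensitivity 46% and 71%, and positive predictive value 70% and 78%.

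**The case against.** The strongest reply is that the objective, primary outcome and hypothesis concern women with MS on average, and a mean contrast answers them. The plan has an effect-modification step by age, its list of tests is given as examples, and sensitivity analyses are promised. The pilot evidence is a contrast by a measured covariate, for which an interaction is the direct response. Most of this stands. It makes the point an addition to a valid primary comparison, and it is why the interaction belongs in the fix. It does not remove the gap: age strata reveal variation only where it follows age, and unspecified sensitivity analyses commit to nothing.

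Four stronger readings are tempting, and the documents do not support them.

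- *A strong effect in a minority would be missed.* In the 20% scenario the mean is usually significant, so the effect is diluted, not absent. Only cancellation hides it, and no passage reports that some women improve while others worsen.
- *The study is aimed at an affected subgroup, or will declare no relation after a null mean.* The protocol speaks of women living with MS, uses migraine as an example, and states no rule for concluding no association.
- *The planned tests carry a 17 to 28% error rate.* The plan does not say how repeated records are handled. A paired test on per-woman contrasts would keep about 5%. The inflation applies to a within-woman model without the random effect.
- *Three cycles from 201 women are assured.* The pilot's 47 women gave more than 4 weeks of data, about 0.8 to 1.2 cycles at the eligible lengths. Fewer completed cycles would lower the power shown.

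One caution about the remedy also stands. If women differ simply in how variable their fatigue is (log-SD 0.3 to 0.5, assumed), simulated tests of τ rejected 7 to 14% at a nominal 5%.

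**Conclusion.** The concern holds as an omission. The plan estimates average phase differences, overall or by age band, and does not estimate how the menstruation effect varies between women, although the design provides replicate cycles. Under the assumed scenarios the consequence is a detected but diluted mean (0.2 SD against 1 SD in affected women), or a zero mean when effects cancel. Leaving the variation out of a within-woman model would also make the interval for the mean too narrow.

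The spread is well estimated only if it is large. Power is about 84 to 85% at SD 0.40 with 201 women and 3 complete cycles, about 19% for a weak minority effect, and lower with serial correlation or missed cycles. A non-significant SD is therefore not evidence that women are alike, and labelling individual women is not justified. All effect sizes are assumptions, because the documents give none. The stated primary comparison remains valid, so this is a cheap exploratory improvement.

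**What to change.** In the Analytical Plan, specify the phase regression as a mixed model with a random intercept and a random menstruation effect for each woman. Beside the mean menstruation difference, report the between-woman SD of that effect with a 95% CI. Add a phase-by-hormonal-contraception interaction from the baseline contraception data, and keep the age stratification.

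Label these results exploratory. State that the SD is to be read from its interval, that a non-significant value does not show homogeneity, and that women will not be classified individually. Name serial correlation, unequal variability between women and incomplete cycles as limits. Do not attach a decision rule that requires a small SD, since the documents offer no threshold for one.

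The cost is a mixed model in place of the simple tests, one or two table rows, and no new data. The interval for the mean widens when women truly differ. At SD 0.40, by the variance formulas above, it is about 1.16 times as wide at 3 cycles and 1.31 times at 6 as in a model that ignores the variation. That wider interval is the correct one. The protocol does not say how many hormonal contraceptive users to expect, so the precision of the interaction is unknown.
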